### 11.3 Power and Sample Size

Since this is a pilot study there will be no formal hypothesis tests performed. With a sample size of 15 evaluable patients (patients must be evaluable for objective response as described in Section 7.1.1), the maximum width of a 95% Clopper Pearson exact confidence interval is 0.52 (since the interval may not be symmetric this corresponds to approximately +/- 0.26 (if the response rate is as high as 7/15). If the response rate is lower than this then the width of the confidence interval will be less. With this sample size we will be able to determine whether the response rate in this treatment is high enough to warrant future examination. Based on preliminary data presented in Table 1 the response rates from previous studies is between 13 and 36% thus we would anticipate that the response rate in this study will need to be at least this high to warrant future studies.

### 11.4 Estimated Accrual Rate

According to the TriNetX tool ([live.trinext.com](http://live.trinext.com)), using the query as defined below, the Wake Forest Baptist Medical Center has seen an average of 2.6 historic arrivals per month over the past 3 years. Using the predicted arrivals tool, 3.5 arrivals per month are expected over the next 1 year. Considering ineligibility and patient declination, we expect to accrue 15 evaluable patients over the course of 2 years. This would correspond to approximately 0.7 patients per month being accrued (meaning 20% of the arrivals per month participating).

Quad-Shot Radiotherapy in Combination with Immune Checkpoint Inhibition for Advanced/Recurrent Head and Neck Cancer  
Wake Forest Baptist Comprehensive Cancer Center  
WFBCCC60320

1547545	pembrolizumab	670
OR		
1597876	nivolumab	670
AND		
C01	Malignant neoplasm of base of tongue	970
OR		
C02	Malignant neoplasm of other and unspecified parts of tongue	1,260
OR		
C03	Malignant neoplasm of gum	320
OR		
C04	Malignant neoplasm of floor of mouth	420
OR		
C05	Malignant neoplasm of palate	340
OR		
C06	Malignant neoplasm of other and unspecified parts of mouth	1,850
OR		
C09	Malignant neoplasm of tonsil	1,100
OR		
C10	Malignant neoplasm of oropharynx	1,020
OR		
C11	Malignant neoplasm of nasopharynx	490
OR		
C12	Malignant neoplasm of pyriform sinus	170
OR		
C13	Malignant neoplasm of hypopharynx	590
OR		
C14	Malignant neoplasm of other and ill-defined sites in the lip, oral cavity and pharynx	560

## 11.5 Estimated Study Length

We anticipate that accrual will be accomplished within 21 months and then follow-up for response can be finished within approximately 3 months, thus this study should be completed within approximately 24 months once accrual commences.

## 12.0 Ethical and regulatory requirements

### 12.1 Ethical conduct of the study

The study will be performed in accordance with ethical principles that have their origin in the Declaration of Helsinki and are consistent with ICH/Good Clinical Practice, and applicable regulatory requirements Subject data protection.

### 12.2 Ethics and regulatory review

Institutional Review Board (IRB) will approve the final study protocol, including the final version of the ICF and any other written information and/or materials to be provided to the patients. The Investigator will ensure the distribution of these documents to the IRB and to the study site staff.

The opinion of IRB should be given in writing.

The protocol should be re-approved by the IRB annually. Before enrollment of any patient into the study, the final study protocol, including the final version of the ICF, should be approved by the

national regulatory authority or a notification to the national regulatory authority should be approved, according to local regulations.

Principal Investigator is responsible for providing the IRB with reports of any serious and unexpected adverse drug reactions from any other study conducted with the IP.

### **12.3 Informed consent**

The Principal Investigator will:

- Ensure that each patient is given full and adequate oral and written information about the nature, purpose, possible risk, and benefit of the study
- Ensure that each patient is notified that he or she is free to discontinue from the study at any time
- Ensure that each patient is given the opportunity to ask questions and allowed time to consider the information provided
- Ensure that each patient provides a signed and dated informed consent before conducting any procedure specifically for the study
- Ensure that the original, signed ICF(s) is/are stored in the Investigator's Study File
- Ensure that a copy of the signed ICF is given to the patient
- Ensure that any incentives for patients who participate in the study as well as any provisions for patients harmed as a consequence of study participation are described in the ICF that is approved by an EC/IRB.

### **Changes to the protocol and informed consent form**

If there are any substantial changes to the study protocol, then these changes will be documented in a study protocol amendment and, where required, in a new version of the study protocol (revised clinical study protocol). The amendment is to be approved by the relevant IRB and, if applicable, the national regulatory authority, before implementation. Local requirements will be followed for revised protocols.

### **12.4 Audits and inspections**

The CCCWFU, a regulatory authority, or IRB may perform audits or inspections at the center, including source data verification. The purpose of an audit or inspection is to systematically and independently examine all study-related activities and documents, to determine whether these

Quad-Shot Radiotherapy in Combination with Immune Checkpoint Inhibition for Advanced/Recurrent Head and Neck Cancer  
Wake Forest Baptist Comprehensive Cancer Center  
WFBCCC60320

activities were conducted, and to determine if data were recorded, analyzed, and accurately reported according to the protocol, GCPs, ICH guidelines, and any applicable regulatory requirements. The Investigator will contact AstraZeneca immediately if contacted by a regulatory agency about an inspection at the center.

## 13.0 Study Management

### 13.1 Training of study site personnel

The Principal Investigator will ensure that appropriate training relevant to the study is given to all of these staff and that any new information relevant to the performance of this study is forwarded to the staff involved.

### 13.2 Data Management

Informed consent document	EPIC
Protocol registration form	WISER/OnCore
Off Study, Off Treatment, Survival	WISER/OnCore
Pre-toxicity	WISER/OnCore
Cycle Tracking	Redcap
Adverse Events Log	WISER/OnCore
Treatment Response Evaluation	Redcap
Evaluation of Best Overall Response	WISER/OnCore
Tumor Measurement	Redcap
PRO-CTCAE	Redcap
Comorbidites	Redcap
Specimen Tracking	Redcap
Tobacco Use	Redcap
Withdrawal of Consent for the Intervention	WISER/OnCore
Follow up post washout	WISER/OnCore
Demographics	Redcap
Medications	Redcap
ECOG Status	WISER/OnCore

### 13.3 Confidentiality and Privacy

Confidentiality will be protected by collecting only information needed to assess study outcomes, minimizing to the fullest extent possible the collection of any information that could directly identify subjects, and maintaining all study information in a secure manner. To help ensure subject privacy and confidentiality, only a unique study identifier will appear on the data collection form. Any collected patient identifying information corresponding to the unique study identifier will be maintained on a linkage file, stored separately from the data. The linkage file will be kept secure, with access limited to

Quad-Shot Radiotherapy in Combination with Immune Checkpoint Inhibition for Advanced/Recurrent Head and Neck Cancer  
Wake Forest Baptist Comprehensive Cancer Center  
WFBCCC60320

designated study personnel. Following data collection subject identifying information will be destroyed (state the anticipated time the data will be destroyed, e.g. three years after closure of the study, and the method of destruction), consistent with data validation and study design, producing an anonymous analytical data set. Data access will be limited to study staff. Data and records will be kept locked and secured, with any computer data password protected. No reference to any individual participant will appear in reports, presentations, or publications that may arise from the study.

#### **13.4 Data Safety and Monitoring**

The principal investigator will be responsible for the overall monitoring of the data and safety of study participants. The principal investigator will be assisted by other members of the study staff.

**The following Appendices are required for all WFBCCC cancer treatment protocols.**

*Add additional appendices as needed.*

**ALL** data collection forms must be included as protocol appendices at the time the protocol is submitted to the WFBCCC Protocol Review Committee (PRC) for review.

## Appendix A – Eligibility Checklist

IRB Protocol No.	WFBCCC Protocol No.
Study Title: Quad-Shot Radiotherapy in Combination with Immune Checkpoint Inhibition for Advanced/Recurrent Head and Neck Cancer	
Principal Investigator: [name]	

Inclusion Criteria (as outlined in study protocol)	Criteria is met	Criteria is NOT met	Source Used to Confirm * (Please document dates and lab results)
Advanced, recurrent or metastatic head and neck squamous cell carcinoma, as defined by clinical or pathological diagnosis of any of the following:			
Locally advanced head and neck squamous cell carcinoma not suitable for curative local treatment.			
Locally recurrent head and neck squamous cell carcinoma not suitable for curative local treatment within or outside a previously irradiated tissue.			
Metastatic head and neck squamous cell carcinoma.			
Target site in the head and neck region amenable to quad-shot palliative radiotherapy, as determined by the treating radiation oncologist.			
Age 18 years or greater at time of registration			
ECOG Performance Status of 0-2.			
Women of child-bearing potential and men must agree to use adequate contraception (hormonal or barrier method of birth control; abstinence) prior to study entry and for the duration of study participation. Should a woman become pregnant or suspect she is pregnant while participating in this study, she should inform her treating physician immediately.			
Ability to understand and the willingness to sign an IRB-approved informed consent document (either directly or via a legally authorized representative).			
Willingness to provide blood and saliva samples for exploratory research purposes			

Quad-Shot Radiotherapy in Combination with Immune Checkpoint Inhibition for Advanced/Recurrent Head and Neck Cancer  
 Wake Forest Baptist Comprehensive Cancer Center  
 WFBCCC60320

Organ and Marrow Function as defined below:													
Absolute neutrophil count (ANC) $\geq 1.5 \times 10^9/L$													
Platelet count $\geq 100 \times 10^9/L$													
Hemoglobin $\geq 9.0 \text{ g/dL}$													
Serum bilirubin $\leq 1.5 \times \text{ULN}$ (institutional upper limit of normal)													
AST and ALT $\leq 2.5 \times \text{ULN}$ (institutional upper limit of normal)													
Serum creatinine CL $>40 \text{ mL/min}$ by the Cockcroft-Gault formula (Cockcroft and Gault 1976) or by 24-hour urine collection for determination of creatinine clearance:		
 
 Males:		
 
 Creatinine CL (mL/min)	= <math>\frac{\text{Weight (kg)} \times (140 - \text{Age})}{72 \times \text{serum creatinine (mg/dL)}}</math>	
 
 Females		
 
 Creatinine CL (mL/min)	= <math>\frac{\text{Weight (kg)} \times (140 - \text{Age})}{72 \times \text{serum creatinine (mg/dL)}} \times 0.85</math>	
 
	Males:		Creatinine CL (mL/min)	= $\frac{\text{Weight (kg)} \times (140 - \text{Age})}{72 \times \text{serum creatinine (mg/dL)}}$	Females		Creatinine CL (mL/min)	= $\frac{\text{Weight (kg)} \times (140 - \text{Age})}{72 \times \text{serum creatinine (mg/dL)}} \times 0.85$			
Males:													
Creatinine CL (mL/min)	= $\frac{\text{Weight (kg)} \times (140 - \text{Age})}{72 \times \text{serum creatinine (mg/dL)}}$												
Females													
Creatinine CL (mL/min)	= $\frac{\text{Weight (kg)} \times (140 - \text{Age})}{72 \times \text{serum creatinine (mg/dL)}} \times 0.85$												
													
													
													
Exclusion Criteria (as outlined in study protocol)		Criteria NOT present	Criteria is present	Source Used to Confirm * (Please document dates and lab results)									
Radiation therapy to the head and neck region within 30 days of registration.													
Prior radiotherapy to the head and neck that precludes safe delivery of study radiotherapy, as determined by the treating radiation oncologist.													
Active medical conditions that are contraindications to study radiotherapy (i.e. scleroderma), as determined by the treating radiation oncologist.													
Pregnant or lactating women are excluded from this study because radiotherapy is contraindicated in pregnancy and because there is an unknown but potential risk for adverse events in nursing infants secondary to treatment of the mother with immunotherapy.													
Participation in another clinical study with an investigational product during the last 3 months.													

Quad-Shot Radiotherapy in Combination with Immune Checkpoint Inhibition for Advanced/Recurrent Head and Neck Cancer  
 Wake Forest Baptist Comprehensive Cancer Center  
 WFBCCC60320

Any previous treatment with a PD1 or PD-L1 inhibitor			
Any anti-cancer therapy (chemotherapy, immunotherapy, endocrine therapy, targeted therapy, biologic therapy, tumor embolization, monoclonal antibodies, other investigational agent) within the last 30 days.			
Mean QT interval corrected for heart rate (QTc) $\geq$ 470 ms. except for patients with pacemaker who have a paced ventricular rhythm			
Current or prior use of immunosuppressive medication within 30 days, with exceptions of intranasal and inhaled corticosteroids or systemic corticosteroids at physiological doses, which are not to exceed 10 mg/day of prednisone, or an equivalent corticosteroid.and with the exception of a short course of prednisone that is prescribed for acute allergic situations or for prevention of an allergy to contrast substance utilized for imaging studies.			
Any unresolved toxicity (>CTCAE grade > 2) from previous anti-cancer therapy. Subjects with irreversible toxicity that is not reasonably expected to be exacerbated by the investigational product may be included (e.g., hearing loss, peripherally neuropathy).			
Any prior Grade $\geq$ 3 immune-related adverse event (irAE) while receiving any previous immunotherapy agent, or any unresolved irAE >Grade 1.			
Active or prior documented autoimmune disease within the past 2 years NOTE: Subjects with vitiligo, Grave's disease, or psoriasis not requiring systemic treatment (within the past 2 years) are not excluded.			
Active or prior documented inflammatory bowel disease (e.g., Crohn's disease, ulcerative colitis).			
History of primary immunodeficiency.			
History of primary immunodeficiency.			
History of hypersensitivity to any excipient in pembrolizumab.			
History of pneumonitis or interstitial lung disease.			
Subjects with uncontrolled seizures.			

Quad-Shot Radiotherapy in Combination with Immune Checkpoint Inhibition for Advanced/Recurrent Head and Neck Cancer  
 Wake Forest Baptist Comprehensive Cancer Center  
 WFBCCC60320

Uncontrolled intercurrent illness including, but not limited to, ongoing or active infection, symptomatic congestive heart failure, uncontrolled hypertension, unstable angina pectoris, uncontrolled cardiac arrhythmia, active peptic ulcer disease or gastritis, active bleeding diatheses, evidence of acute or chronic hepatitis B, hepatitis C or human immunodeficiency virus (HIV), or psychiatric illness/social situations that would limit compliance with study requirements or compromise the ability of the subject to give written informed consent.			
Known history of active tuberculosis.			
Receipt of live attenuated vaccination within 30 days prior to study entry or within 30 days of receiving pembrolizumab.			
Any condition that, in the opinion of the investigator, would interfere with evaluation of study treatment or interpretation of patient safety or study results.			

This subject is  eligible /  ineligible for participation in this study.

OnCore Assigned PID: \_\_\_\_\_

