### **3.1 Inclusion Criteria**

- 3.1.1 Advanced, recurrent or metastatic head and neck squamous cell carcinoma, as defined by clinical or pathological diagnosis of any of the following:
  - 3.1.1.1 Locally advanced head and neck squamous cell carcinoma not suitable for curative local treatment.
  - 3.1.1.2 Locally recurrent head and neck squamous cell carcinoma not suitable for curative local treatment within or outside a previously irradiated tissue.
  - 3.1.1.3 Metastatic head and neck squamous cell carcinoma.

Quad-Shot Radiotherapy in Combination with Immune Checkpoint Inhibition for  
Advanced/Recurrent Head and Neck Cancer  
Wake Forest Baptist Comprehensive Cancer Center  
WFBCCC60320

- 3.1.2 Target site in the head and neck region amenable to quad-shot palliative radiotherapy, for which palliative radiotherapy is recommended, as determined by the treating radiation oncologist.
- 3.1.3 Age 18 years or greater at time of registration
- 3.1.4 ECOG Performance Status of 0-2.
- 3.1.5 Women of child-bearing potential and men must agree to use adequate contraception (hormonal or barrier method of birth control; abstinence) prior to study entry and for the duration of study participation. Should a woman become pregnant or suspect she is pregnant while participating in this study, she should inform her treating physician immediately.
- 3.1.6 Ability to understand and the willingness to sign an IRB-approved informed consent document (either directly or via a legally authorized representative).
- 3.1.7 Willingness to provide blood and saliva samples for exploratory research purposes
- 3.1.8 Organ and Marrow Function as defined below:
  - 3.1.8.1 Absolute neutrophil count (ANC)  $\geq 1.5 \times 10^9/L$
  - 3.1.8.2 Platelet count  $\geq 100 \times 10^9/L$
  - 3.1.8.3 Hemoglobin  $\geq 9.0 \text{ g/dL}$
  - 3.1.8.4 Serum bilirubin  $\leq 1.5 \times \text{ULN}$  (institutional upper limit of normal)
  - 3.1.8.5 AST and ALT  $\leq 2.5 \times \text{ULN}$  (institutional upper limit of normal)
  - 3.1.8.6 Serum creatinine CL  $> 40 \text{ mL/min}$  by the Cockcroft-Gault formula (Cockcroft and Gault 1976) or by 24-hour urine collection for determination of creatinine clearance:

Males:

$$\text{Creatinine CL (mL/min)} = \frac{\text{Weight (kg)} \times (140 - \text{Age})}{72 \times \text{serum creatinine (mg/dL)}}.$$

Females:

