### 3.2 Exclusion Criteria

- 3.2.1 Radiation therapy to the planned quad-shot radiotherapy target region within 30 days of registration.
- 3.2.2 Prior radiotherapy to the head and neck that precludes safe delivery of study radiotherapy, as determined by the treating radiation oncologist.
- 3.2.3 Active medical conditions that are contraindications to study radiotherapy (i.e. scleroderma), as determined by the treating radiation oncologist.
- 3.2.4 Pregnant or lactating women are excluded from this study because radiotherapy is contraindicated in pregnancy and because there is an unknown but potential risk for adverse events in nursing infants secondary to treatment of the mother with immunotherapy.
- 3.2.5 Participation in another clinical study with an investigational product during the last 3 months.
- 3.2.6 Any previous treatment with a PD1 or PD-L1 inhibitor.
- 3.2.7 Any anti-cancer therapy (chemotherapy, immunotherapy, endocrine therapy, targeted therapy, biologic therapy, tumor embolization, monoclonal antibodies, other investigational agent) within the last 30 days. Note: this excludes palliative radiotherapy to the non-target site.
- 3.2.8 Mean QT interval corrected for heart rate (QTc)  $\geq 470$  ms. except for patients with pacemaker who have a paced ventricular rhythm
- 3.2.9 Current or prior use of immunosuppressive medication within 30 days, with exceptions of intranasal and inhaled corticosteroids, a brief, non-sustained corticosteroids treatment for incidental problems such as allergies (at the discretion of the treating physician) or sustained systemic corticosteroids treatment at physiological doses, which are not to exceed 10 mg/day of prednisone, or an equivalent corticosteroid except for a short course of prednisone that is prescribed for acute allergic situations or for prevention of an allergy to contrast substance utilized for imaging studies.
- 3.2.10 Any unresolved toxicity (>CTCAE grade > 2) from previous anti-cancer therapy. Subjects with irreversible toxicity that is not reasonably expected to be exacerbated by the investigational product may be included (e.g., hearing loss, peripherally neuropathy).
- 3.2.11 Any prior Grade  $\geq 3$  immune-related adverse event (irAE) while receiving any previous immunotherapy agent, or any unresolved irAE >Grade 1.

Quad-Shot Radiotherapy in Combination with Immune Checkpoint Inhibition for  
Advanced/Recurrent Head and Neck Cancer  
Wake Forest Baptist Comprehensive Cancer Center  

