WFBCCC60320

- 3.2.12 Active or prior documented autoimmune disease within the past 2 years  
NOTE: Subjects with vitiligo, Grave's disease, or psoriasis not requiring systemic treatment (within the past 2 years) are not excluded.
- 3.2.13 Active or prior documented inflammatory bowel disease (e.g., Crohn's disease, ulcerative colitis).
- 3.2.14 History of primary immunodeficiency.
- 3.2.15 History of allogeneic organ transplant.
- 3.2.16 History of hypersensitivity to any excipient in pembrolizumab.
- 3.2.17 History of pneumonitis or interstitial lung disease.
- 3.2.18 Subjects with uncontrolled seizures.
- 3.2.19 Uncontrolled intercurrent illness including, but not limited to, ongoing or active infection, symptomatic congestive heart failure, uncontrolled hypertension, unstable angina pectoris, uncontrolled cardiac arrhythmia, active peptic ulcer disease or gastritis, active bleeding diatheses, evidence of acute or chronic hepatitis B, hepatitis C or human immunodeficiency virus (HIV), or psychiatric illness/social situations that would limit compliance with study requirements or compromise the ability of the subject to give written informed consent.
- 3.2.20 Known history of active tuberculosis.
- 3.2.21 Receipt of live attenuated vaccination within 30 days prior to study entry or within 30 days of receiving pembrolizumab.
- 3.2.22 Any condition that, in the opinion of the investigator, would interfere with evaluation of study treatment or interpretation of patient safety or study results.

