## 4.0 Methods

### 4.1 Registration Procedure

All patients entered on any WFBCCC trial, whether treatment, companion, or cancer control trial, **must** be linked to the study in EPIC within 24 hours of Informed Consent. Patients **must** be registered prior to the initiation of treatment.

You must perform the following steps in order to ensure prompt registration of your patient:

1. Complete the Eligibility Checklist (Appendix A)
2. Complete the Protocol Registration Form (Appendix B)
3. Alert the Cancer Center registrar by phone, *and then* send the signed Informed Consent Form, Eligibility Checklist and Protocol Registration Form to the registrar, either by fax or e-mail.

\*Protocol Registration is open from 8:30 AM - 4:00 PM, Monday-Friday.

4. Fax/e-mail ALL eligibility source documents with registration. Patients **will not** be registered without all required supporting documents.

Note: If labs were performed at an outside institution, provide a printout of the results. Ensure that the most recent lab values are sent.

To complete the registration process, the Registrar will:

- assign a patient study number
- register the patient on the study

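### The Appendix A eligibility checklist omits the allogeneic transplant exclusion (3.2.15), printing another row twice in its place, and words several other criteria differently from Section 3

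*Combined protocol and SAP*

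**What the plan says.** Section 4.1 (Registration Procedure) opens its list of steps with "Complete the Eligibility Checklist (Appendix A"), and the completed form goes to the registrar with the signed consent. The exclusion block of Appendix A is headed "Exclusion Criteria (as outlined in study protocol"), so staff are told that it restates Section 3. The form ends in an eligible/ineligible decision.

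Section 3.2.14 excludes primary immunodeficiency, once. Section 3.2.15 then excludes "History of allogeneic organ transplant". Appendix A prints "History of primary immunodeficiency" on two consecutive rows and contains no transplant row.

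On recent radiotherapy, Section 3.2.1 reads "Radiation therapy to the planned quad-shot radiotherapy target region within 30 days of registration", while the Appendix A row reads "Radiation therapy to the head and neck region within 30 days of registration". Section 3.2.7, on other anti-cancer therapy within 30 days, ends with "Note: this excludes palliative radiotherapy to the non-target site"; the Appendix A row stops before that note.

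**The concern.** A checklist is the working instrument of eligibility: the person completing it answers the rows that are there. If a row is missing, that criterion is checked only when someone goes back to Section 3 or notices the history by another route.

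The missing row concerns safety. Under severe and fatal immune-mediated reactions, Section 8.1 lists solid organ transplant rejection among reactions to checkpoint inhibitors seen in under 1% of patients, and adds that some of the listed reactions have had severe or fatal cases. The protocol thus states both the exclusion and the hazard, and its own form does not ask the question.

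The radiotherapy mismatch works the other way. A stricter row on the form can hold back a patient whom Section 3 would accept. Two wordings of one criterion also leave it unclear which of them a registration should be audited against.

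**Working it through.** There is no figure to recompute. The check is a row-by-row comparison of Section 3 with Appendix A.

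**1. Count.** Section 3.2 runs from 3.2.1 to 3.2.22, which is 22 criteria. Appendix A has 22 exclusion rows. One is a repeat, so distinct criteria = 22 − 1 = 21, and the criterion absent is 3.2.15. That is 1 of 22 exclusions with no prompt on the form.

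**2. Position of the repeat.**

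| Section 3.2 | Appendix A, same position |
|---|---|
| 3.2.13 inflammatory bowel disease | inflammatory bowel disease |
| 3.2.14 primary immunodeficiency | primary immunodeficiency |
| 3.2.15 allogeneic organ transplant | primary immunodeficiency (repeated) |
| 3.2.16 hypersensitivity to a pembrolizumab excipient | hypersensitivity to a pembrolizumab excipient |

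The repeat fills exactly the 3.2.15 slot, and no transplant wording appears anywhere else on the form.

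**3. Recent radiotherapy (3.2.1).** Section 3.1.2 requires a "Target site in the head and neck region amenable to quad-shot palliative radiotherapy", so the planned target region lies inside the head and neck region. Anyone barred by 3.2.1 is therefore also barred by the checklist row. The checklist additionally bars patients whose radiotherapy in the previous 30 days went to a head and neck site outside the planned target. This row can delay or refuse a patient; it cannot admit one whom 3.2.1 excludes.

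**4. Other wording differences.**

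| Criterion | Difference in Appendix A | Direction |
|---|---|---|
| 3.1.2 | Drops the requirement that palliative radiotherapy be recommended | Looser on its face |
| 3.2.7 | Drops the note on palliative radiotherapy to a non-target site | Stricter, or no change |
| 3.2.9 | Drops the allowance for brief corticosteroid treatment of incidental problems at the physician's discretion; keeps the short prednisone course for acute allergy or contrast | Stricter |

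For 3.2.7, the bracketed list of therapies does not name radiotherapy in either version. If the list is exhaustive, losing the note changes nothing. If it is only illustrative, losing the note could bar more patients.

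Section 3.2.2, on prior radiotherapy that precludes safe delivery, is worded the same in both places.

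**5. Tally.** One criterion is absent (3.2.15) and four are worded differently (3.1.2, 3.2.1, 3.2.7, 3.2.9), so five do not match.

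**The case against.** The strongest reply is that the form is not the only safeguard.

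- The immunosuppressant row would stop a recipient on such medication within 30 days beyond the listed steroid exceptions.
- The last row bars any condition that the investigator thinks would interfere with interpreting patient safety.
- Section 4.1 refuses registration without the eligibility source documents, and the Section 6.1 calendar requires a medical and surgical history at screening.
- Section 6.6 allows removal of a subject found to have met an exclusion at entry where continuing might be a safety risk.

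This stands in part: the gap is narrower than the missing row alone suggests. But the immunosuppressant row looks back only 30 days and exempts systemic corticosteroids up to 10 mg/day of prednisone or equivalent. The investigator row depends on opinion. A history taken at screening does not by itself prompt a comparison with 3.2.15. Removal under 6.6 comes after entry.

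A second reply is that the Appendix B registration form also speaks of completing the checklist in WISER. The documents do not show that version, and it may be correct. This stands, and it is why the electronic form needs its own check.

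A reader might also infer that the radiotherapy rows admit ineligible patients, or that they slow a trial planned at about 0.7 patients per month. The documents support neither. The broader row only bars more patients, a 30-day window may postpone registration rather than end it, and no frequency of recent non-target head and neck radiotherapy is given.

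**Conclusion.** The point holds. As printed, the registration checklist does not prompt a check of exclusion 3.2.15 for any patient registered on it, and the backstops are partial. This omission is what makes the correction necessary. The 3.2.1 mismatch is secondary, and the differences in 3.1.2, 3.2.7 and 3.2.9 are matters of reconciliation; the 3.2.7 note may have no effect at all.

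It would be tempting to conclude that transplant recipients have been, or will be, registered. The documents do not show that: they contain no registration data, and some recipients would be stopped by other rows or by record review.

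The endpoint definition, the exact confidence interval and the target of 15 evaluable patients do not change. What is affected is who may enter.

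Two assumptions remain. One is that the repeated row is in the source page and not a product of text extraction; the matching count of 22 and the exact position make this likely, and one look at the page settles it. The other is that staff use the printed Appendix A, or a WISER version with the same content.

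**What to change.** - Confirm the repeated row on the source page, then replace the second primary immunodeficiency row in Appendix A with the text of 3.2.15.
- Reconcile 3.1.2, 3.2.1, 3.2.7 (note) and 3.2.9 so that Section 3 and Appendix A carry one wording. Which wording is clinically intended is for the investigators to decide; this review does not choose.
- Make the same row-by-row check on the WISER checklist mentioned in Appendix B.
- Check every patient already registered against 3.2.15 and document the result.

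The cost is a corrected form, a short administrative amendment and a brief record check. Sample size and analysis are unaffected.
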